The recommendation for males to store sperm before taking part in the study has been removed, and replaced with guidance for male subjects to withdraw if they intend to father a child.

Applicable Sections:

Section 4.4 Potential risks and benefits

Section 4.5.3.1.2 Precautions for sexual intercourse: male subjects

Amendment 2 (General)

Interactions

- The information on interaction with transporters in nonclinical studies has been updated.
- The clinical safety and clinical pharmacokinetics sections have been updated based on recent data from two drug-drug interaction studies, one study with itraconazole and voriconazole, and one study with pirfenidone and nintedanib. Increased exposures of nintedanib, one of the standard of care treatments for IPF, was observed when coadministered with GLPG1690.
- Additional PK sampling has been introduced to assess nintedanib levels.
- A population PK analysis for nintedanib and pirfenidone has been added in the Statistical methods section.

Applicable Sections:

Section 2.1.3 Nonclinical pharmacokinetics and product metabolism

Section 2.2.1 Clinical Safety

Section 2.2.2 Clinical Pharmacokinetics

Section 4.4 Potential risks and benefits

Section 6.1 Timing of assessments

Section 6.3 Initial subject and disease characteristics

Section 6.4 Subject diary card

Section 6.7 Pharmacokinetic assessments

Section 6.11 Schedule of activities

Section 7.3.6 Pharmacokinetics [REDACTED]

The QTcF thresholds leading to discontinuation have been clarified, and the following has been added:

- “If a normal QTcF is reported during the visit, but the central cardiologist reports it as abnormal (any of the two criteria above), then the IMP should be discontinued as soon as possible”

Applicable Sections:

Section 4.5.4 Treatment discontinuation, subject withdrawal, and study termination

The list of clinical laboratory tests has been revised

- Mean corpuscular volume (MCV), mean corpuscular hemoglobin (MCH), and mean corpuscular hemoglobin concentration (MCHC) have been added to the hematology parameters to reflect the standard panel of investigations typically used in the IPF patient population.
- If creatine kinase (CK) is elevated, then CK-muscle/brain (CK-MB) is to be measured, to monitor for muscle breakdown indicative of coronary heart disease.
- Amylase and lipase have been added to monitor risk of pancreatitis, a reported risk/ adverse drug reaction for nintedanib.

Applicable Section:

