The use of medication known to prolong QT interval during the study needs to be based on a benefit-risk evaluation by the investigator, e.g. in the case of atrial fibrillation. In certain other situations (e.g. the initiation of macrolides or fluoroquinolones in case of a lower respiratory tract infection), when the benefit-risk evaluation necessitates the administration of medication known to or potentially prolonging QT, IMP can be interrupted as evaluated by the investigator after clinical assessment of the subject's profile, including the baseline QTcF and how this has changed over time for this specific subject. If the investigator elects to continue IMP, additional monitoring will be performed as per investigator's judgment. A non-exhaustive list of medication known to prolong QT interval is provided in [Appendix 7](#).

Precautions with other concomitant medications

At dose levels of 600 mg q.d., GLPG1690 has the potential to influence substantially the metabolism of substrates of CYP2C8 and to potentially be influenced by known strong CYP3A4/potent P-gp inducers/inhibitors.

- GLPG1690 demonstrated a strong time-dependent inhibition potential against CYP2C8-mediated metabolism. Consequently, GLPG1690 should not be used concomitantly with medications primarily or solely metabolized via CYP2C8 (see [Appendix 3](#)). For other medications involving part of their metabolism pathway via CYP2C8, caution should be applied on a case-by-case basis taking into consideration the benefit/risk ratio. Statins such as fluvastatin and pitavastatin are metabolized to some degree by CYP2C8, and need to be used with caution. Other statins such as simvastatin, lovastatin, and atorvastatin are theoretically less metabolized by CYP2C8. Monitoring of LFTs and creatine kinase is implemented during the study, and guidance to the subject aligned with guidance for statins in clinical practice is therefore strongly recommended. Loperamide is also a substrate of CYP2C8, and special caution should be applied in alignment with clinical practice.

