6.6.2. Clinical Laboratory Evaluations

Blood samples will be collected before IMP intake by venipuncture (or indwelling catheter) at the time points indicated in the Schedule of Activities provided in Section 6.11 (see also Section 6.1). In addition, urine samples for the clinical laboratory evaluations will be collected.

Subjects do not need to be fasted at the time of sampling, unless specifically indicated. Clinical laboratory evaluations will be performed by the central laboratory.

Blood and urine samples will be collected for the following clinical laboratory safety tests:

- Hematology: hematocrit, mean corpuscular volume (MCV), mean corpuscular hemoglobin (MCH), mean corpuscular hemoglobin concentration (MCHC), Hb, red blood cell count, white blood cell (WBC) count, WBC differential count (absolute and relative), and platelets.
- Coagulation: activated partial thromboplastin time and prothrombin time, INR.
- Clinical chemistry: random glucose, urea, creatinine, uric acid, sodium, potassium, calcium, chloride, phosphorus, AST, ALT, GGT, total bilirubin, alkaline phosphatase, lactate dehydrogenase, total serum bile acid, albumin, total proteins, triglycerides, cholesterol, high density lipoprotein, low density lipoprotein, amylase, lipase, low density lipoprotein, and creatine kinase (CK) (CK- muscle/brain [CK-MB] to be performed if CK is elevated).
- Urinalysis:
 - Dipstick: pH, glucose, proteins, blood, leucocytes;
 - Microscopic examination of the sediment (cylinders, erythrocytes, leucocytes), if indicated.
- Serology: hepatitis B surface antigen and hepatitis C antibody, and HIV 1 and HIV 2 antibodies only at screening. Positive hepatitis and HIV results should be reported by the investigator as required by local law. To assess eligibility, a positive hepatitis C antibody test should be confirmed by hepatitis C virus (HCV) RNA test.
- FSH test for females at screening to confirm menopause, if applicable.
- Urine pregnancy tests will be performed (only for WOCBP) on a monthly basis at home or at the clinical study center, with one additional test at the clinical study center at Visit 4. At screening, a serum pregnancy test (beta-human chorionic gonadotropin) will be performed. A positive urine pregnancy test needs to be confirmed as soon as possible by a serum pregnancy test (local sample; central sample to be sent as well).

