### 7.2. Calculation of Percentages

For event-type data (e.g. adverse events), the denominator for calculation of percentages will be all subjects in the analysis set and analysis period. For other data (e.g. worst-case analysis of assessments, demographic data), the denominator will be all subjects with (postbaseline) data for the parameter, in the analysis set and analysis window/period. Missing values will not be included in the denominator count.

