#### 9.4.2.5. Scoring Based on CTCAE/Other Gradings

CTCAE version 5.0 classification is only for the tests listed below.

Tests	Thresholds (Conventional Unit		Thresho (SI Unit	Thresholds (SI Units)		
Hematology						
Hemoglobin (anemia) decreased	<lln-10< td="">g/dL	<lln-100< td="">g/L	G1	</lln-100<>	</lln-10<>	g/dL	<lln-100< td="">g/L	G1	</lln-100<>	g/L	G1	
	<10 - 8 <8	g/dL g/dL	<100 -80 <80	g/L g/L	G2 G3	
Hemoglobin increased (increase above ULN)	Increase >0-2	g/dL	Increase >0-20	g/L	G1	
	Increase >2-4 Increase>4	g/dL g/dL	Increase >20-40 Increase>40	g/L g/L	G2 G3	
White blood cell (WBC) count decreased	<lln-3000< td="">/mm3	<lln-3.0< td="">* 10^9/L	G1	</lln-3.0<>	</lln-3000<>	/mm3	<lln-3.0< td="">* 10^9/L	G1	</lln-3.0<>	* 10^9/L	G1	
	<3000 - 2000 < 2000-1000 <1000	/mm3 /mm3 /mm3	<3.0-2.0 < 2.0-1.0 <1.0	* 10^9/L * 10^9/L * 10^9/L	G2 G3 G4	
White blood cell (WBC) count increased	>100,000	/mm3	>100.0	* 10^9/L	G3	
Neutrophils decreased	< LLN-1500	/mm3	< LLN-1.5	* 10^9/L * 10^0/I	G1 G2	
	< 1000-500	/mm3	< 1.0-0.5	* 10^9/L * 10^9/L * 10^0/L	G2 G3	
Lymphocytes decreased	< 500	/mm3	< 0.5	* 10^9/L * 10^9/L	G4 G1	
	< 800-500 < 500-200	/mm3 /mm3	< 0.8-0.5 < 0.5-0.2	* 10^9/L * 10^9/L	G2 G3	
	< 200	/mm3	< 0.2	* 10^9/L	G4	
Lymphocytes increased	> 4000 > 20,000	/mm3 /mm3	> 4.0 > 20.0	* 10^9/L * 10^9/L	G2 G3	
Eosinophils absolute count	>ULN		>ULN		G1	
Eosinophils relative count	> 7%		> 7%		G1	
Platelets decreased	< LLN-75000	/mm3	< LLN-75.0	* 10^9/L	G1	

CONFIDENTIAL

Doc id 402993

	< 75000 – 50000	/mm3	< 75.0 - 50.0	* 10^9/L	G2
	< 50000-25000	/mm3	< 50.0-25.0	* 10^9/L	G3
	< 25000	/mm3	< 25.0	* 10^9/L	G 4
Coagulation					
Activated partial	> ULN - 1.5 x UL	N	> ULN - 1.5 x U	LN	Gl
thromboplastin time	> 1.5 - 2.5 x ULN	[	> 1.5 - 2.5 x ULN		G2
(aPTT)	> 2.5  x ULN		> 2.5  x ULN		G3
	> ULN - 1.5 x UL	N	> ULN - 1.5 x U	LN	
Prothrombin time (PT)	> 1.5 - 2.5 x ULN		> 1.5 - 2.5 x ULM	V	/
	> 2.5 x ULN		> 2.5 x ULN		
	1.2 – 1.5 xULN		> 1.2 - 1.5 xULN	1	G1
INR increased	> 1.5 - 2.5 xULN		> 1.5 - 2.5 xULN	ſ	G2
	> 2.5 xULN		> 2.5  xULN		G3
Chemistry					
Glucose decreased	< LLN – 55	mg/dL	< LLN - 3.0	mmol/L	G1
	< 55 - 40	mg/dL	< 3.0-2.2	mmol/L	G2
	< 40 - 30	mg/dL	< 2.2 -1.7	mmol/L	G3
	< 30	mg/dL	< 1.7	mmol/L	G4
Glucose increased (fasting)	> 130	mg/dL	> 7.2	mmol/L	/
	> ULN - 1.5 x UL	Ŋ	> ULN - 1.5 x U	G1	
Constitution in success 1	>1.5-3x ULN		>1.5-3x ULN		G2

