# 9.4.2.8. Analyses

No formal inferential statistics (p-values) will be derived.

For each laboratory test, descriptive statistics and graphical presentation (line plot of the mean and SE) will be provided for the actual laboratory values and change from baseline over time-by-treatment group.

A summary table per laboratory test category (hematology, biochemistry, urinalysis and coagulation), laboratory test and unit, treatment group and time point, showing only the mean value of actual values and changes from baseline will also be provided.

All laboratory abnormalities after the first dose of IP up to 30 days after the last dose will be included, consistently with AE reporting.

A shift table per laboratory test category (hematology, biochemistry, urinalysis and coagulation), laboratory test and treatment group will be provided for laboratory tests with normal ranges, for which CTCAE grades are not available. The table will present the worst shift in abnormality (L/N/...) during the treatment period versus the baseline abnormality (L/N/H).

Frequency table will be provided of the worst treatment-emergent laboratory abnormalities per laboratory test category (hematology, biochemistry, urinalysis and coagulation), laboratory test, and treatment group. This table will be created for those laboratory tests for which CTCAE grades are not available.

A shift table per laboratory test category (hematology, biochemistry and coagulation), laboratory test and treatment group for CTCAE grades will also be provided for selected tests only. The table will present the worst shift in CTCAE toxicity grade during the treatment period versus the baseline value.

A frequency table of the worst treatment-emergent laboratory CTCAE toxicity grades per laboratory test category (hematology, biochemistry and coagulation), laboratory test, and treatment group will be provided for selected tests only.

Shift table per laboratory test category (hematology, biochemistry, and urinalysis), laboratory test, and treatment group for laboratory tests with categorical data. The table will present the worst shift in value during the treatment period versus the baseline value.

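### CK-MB percentages are taken over subjects tested because their CK was elevated, and amylase and lipase get no severity categories, so the by-arm laboratory tables can misstate the first and do not count marked elevations of the other two

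*Protocol*

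**What the plan says.** The protocol's Summary of Changes for Amendment 2 gives the purpose of each added test. For CK-MB it says "If creatine kinase (CK) is elevated, then CK-muscle/brain (CK-MB) is to be measured", which is meant to pick up muscle breakdown pointing to coronary disease. For the pancreatic enzymes it says "Amylase and lipase have been added to monitor risk of pancreatitis, a reported risk/ adverse drug reaction for nintedanib". The current text in Protocol 6.6.2 agrees: amylase and lipase belong to the routine chemistry panel, with "CK- muscle/brain [CK-MB] to be performed if CK is elevated". The schedule footnotes repeat the condition.

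The SAP handles these tests as follows.

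- **Denominator (SAP 7.2).** For worst-case analyses of assessments, "the denominator will be all subjects with (postbaseline) data for the parameter, in the analysis set and analysis window/period". Missing values are left out. Adverse event percentages use all subjects in the analysis set and period.
- **Grading (SAP 9.4.2.5).** "CTCAE version 5.0 classification is only for the tests listed below". CK is in the table with four grades. CK-MB, amylase and lipase are not.
- **Ungraded tests (SAP 9.4.2.4, 9.4.2.7.1, 9.4.2.8).** They are scored low, normal or high, and one high value after baseline makes the subject high. Of the frequency table of treatment-emergent abnormalities the SAP says "This table will be created for those laboratory tests for which CTCAE grades are not available".
- **All laboratory tests (SAP 7.1, 9.4.2.8).** Mean, median, minimum and maximum of values and changes, and mean plots, are given by arm and time point.

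**The concern.** Whether a subject has a CK-MB result depends on a CK result obtained after randomisation. Treatment could affect that: Protocol 4.5.3.2 describes strong CYP2C8 inhibition, names statins partly cleared by that enzyme, and adds "Monitoring of LFTs and creatine kinase is implemented during the study". If more subjects on active drug reach an elevated CK, more of them enter the CK-MB denominator. The two percentages then compare differently selected subjects, and the randomisation no longer protects the comparison.

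Baseline adds a second difficulty. A subject with normal CK before dosing has no baseline CK-MB. Under SAP 9.4.2.7.1 any later high value in that subject counts as treatment-emergent, while a change from baseline exists only for subjects whose CK was already elevated before dosing. Summaries of values and of changes therefore describe different subsets.

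For amylase and lipase the denominator is sound, because they belong to the panel taken at every laboratory visit. What is lost is degree: a value just above the upper limit and one many times above it fall into the same category. The question these tests were added to answer, how many subjects per arm had marked elevations, has no table. It matters here because Protocol 2.2.2 and 4.4 report that nintedanib exposure roughly doubled when taken together with 600 mg GLPG1690, and less when the doses were separated.

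**Working it through.** The plan gives no figure for this point, so there is none to reproduce. The only documented input is 250 subjects per arm (Protocol 7.1). All event counts below are assumed, because the documents give no rates for CK, CK-MB, amylase or lipase.

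**CK-MB.** For each arm let t be the number tested (CK elevated) and h the number with high CK-MB. The SAP percentage is h/t and the whole-arm percentage is h/250. It follows that

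whole-arm ratio = (ratio of CK-elevation rates) × (ratio of h/t).

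The two ratios agree only if CK is elevated equally often in both arms.

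| Case | Active h/t | Placebo h/t | SAP percentages (ratio) | Whole-arm percentages (ratio) |
|---|---|---|---|---|
| a | 12/50 | 8/25 | 24.0 v 32.0 (0.75) | 4.8 v 3.2 (1.50) |
| b | 10/50 | 5/25 | 20.0 v 20.0 (1.00) | 4.0 v 2.0 (2.00) |
| c | 25/50 | 10/25 | 50.0 v 40.0 (1.25) | 10.0 v 4.0 (2.50) |
| d | 10/25 | 5/25 | 40.0 v 20.0 (2.00) | 4.0 v 2.0 (2.00) |

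Check of case a: the CK-elevation ratio is (50/250)/(25/250) = 2, and 2 × 0.75 = 1.50. Case a reverses the direction, b cancels the excess, c halves the ratio, and d, with equal CK rates, shows no distortion.

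**Amylase and lipase.** Suppose 25 of 250 subjects (10.0%) are high in each arm. The frequency table shows no difference. Those 25 could include 10 subjects at or above 3×ULN in one arm and 1 in the other, which is 10/250 = 4.0% against 1/250 = 0.4% (Fisher p = 0.011, given only as a sense of scale, since the plan tests no laboratory result). Would the mean reveal it? If 9 subjects are at 4× rather than 1.5×ULN, the arm mean moves by 9 × (4 − 1.5)/250 = 0.09×ULN at one time point. The maximum would show that an extreme value occurred, but not how many subjects had one.

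**Background of trivial high values.** Assume the normal range cuts off the top 2.5% in unaffected subjects, with nine post-baseline visits to Week 52 (Visits 4 to 12). If values are independent, the chance of at least one high value is 1 − 0.975^9 = 20.4%, about 51 of 250. With equicorrelated normal values, simulation gives about 13.5%, 10% and 8.3% at within-subject correlations of 0.5, 0.7 and 0.8; the last is about 21 of 250. Leaving out subjects already high at baseline, as the treatment-emergent rule requires, the range is about 6% (correlation 0.8) to 20% (independence; 0.975 × 20.4% = 19.9%). A handful of marked elevations would sit among roughly 15 to 50 trivial ones per arm.

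**The case against.** A reader might infer that an excess would be hidden altogether, or that amylase and lipase are reported only as above normal and could also be reversed. The documents do not support this.

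- Protocol 7.3.1 and SAP 9.4 require counts with percentages. In case a the row would read 12 (24.0%) against 8 (32.0%), so the excess is visible to a reader who looks at the counts.
- The selecting step is itself reported: CK is measured in all subjects and graded, although SAP 9.4.2.8 limits the grade tables to selected tests.
- Every laboratory test gets medians and maxima, so a very high lipase value would appear.
- Clinically significant abnormalities become adverse events (Protocol 6.6.2), tabulated over all subjects. SAP 9.4.1.6.4 adds tables for events of interest to nintedanib, from a list still to be completed.
- Amylase and lipase have no denominator problem, so nothing can be reversed for them.

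It is also fair to say that the grading table was revised with clinicians (SAP version history), that laboratory results are only described, and that this SAP serves an abbreviated report after the programme was stopped.

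All of this limits the consequence. It does not repair the percentage, which can point the opposite way to the count beside it. Adverse event capture rests on the investigator's judgement, whereas the tests were added for systematic monitoring. Safety is among the few analyses kept after termination, and pooling with the sister study was dropped, so the by-arm tables of each study carry more weight.

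**Conclusion.** The point holds in a limited form. Following the SAP gives a CK-MB percentage within a group selected after randomisation. It can attenuate, cancel or reverse a between-arm difference, but only if CK-elevation rates differ between arms. The size is unknown; ratios of 0.75 against 1.50, or 1.00 against 2.00, are illustrations from assumed counts. Part of any excess would still appear in the counts, the CK results and the adverse events.

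For amylase and lipase the defect is narrower: the shift and frequency tables have no severity category, so the number of subjects per arm with marked elevations is not reported.

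One uncertainty remains. SAP 9.4.2 only lists tests outside the planned panels and does not say whether a conditional test counts as planned. If CK-MB were merely listed, there would be no misleading percentage, but no whole-arm rate either. This is a worthwhile, inexpensive correction to safety reporting and has no bearing on the efficacy conclusions.

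**What to change.** **CK-MB (SAP 7.2 and 9.4.2.8).** State that CK-MB is tabulated. Report elevations by arm over all FAS subjects with at least one post-baseline CK result. Beside them show the number with elevated CK, the number tested for CK-MB, and the number with elevated CK but no CK-MB result. Keep that last group as its own row and do not count it as normal. State which CK level counts as elevated for this table, since the documents do not define it. Do not compare CK-MB means or changes from baseline between arms.

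**Amylase and lipase (SAP 9.4.2.5).** Add multiples-of-ULN categories, of the kind the SAP already uses for CK and the liver enzymes, with cut-offs agreed with the clinicians. Tabulate the worst treatment-emergent category by arm. Part of the study team was unblinded after termination (SAP 2.7), so the cut-offs should be fixed without sight of these results by arm, or the change recorded in the study report as SAP 9.1 requires.

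**Cost.** SAP wording and a few table rows; no new data. Subjects never tested because their CK stayed normal are taken to have no CK-MB elevation, and a footnote should say so.

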Appendix 4 Known strong CYP3A4 inducers and potent P-gp inducers

Voriconazole, a strong CYP3A4 inhibitor, has been added to the non-exhaustive list of strong CYP3A4 inhibitors in Appendix 5.

Applicable Section

Appendix 5 Known strong CYP3A4 inhibitors

Amendment 1 [REDACTED]**The overall reason for this amendment:**

Changes to accommodate requests from the [REDACTED]
[REDACTED] Ethics Committee

Eligibility criteria:

- Inclusion criterion 6 has been modified (under number 6.1) to require stability of the patients' standard of care (pirfenidone or nintedanib) treatment during the 2 months before screening and during the screening period. The requirements for stability of concomitant therapies for long-term treatment of pre-existing conditions, as well as for pirfenidone and nintedanib treatment, in Section 4.5.3.2 Prior and Concomitant Medications has been updated.
- Exclusion criterion 21 was updated (under number 21.1) with the following text [REDACTED]
[REDACTED]
"as well as any subjects falling into any of the categories of persons listed by applicable law and regulations as protected persons for which participation in a study is prohibited or subject to restrictions."
- Exclusion criterion 22 was modified (under number 22.1) to exclude patients with moderate to severe hepatic impairment (Child-Pugh B or C).

Applicable Sections:

Section 4.5.1 Inclusion criteria

Section 4.5.2 Exclusion criteria

Section 4.5.3.2 Prior and concomitant medications

Amendment 1**The overall reason for this amendment:**

Changes to accommodate requests made under the [REDACTED]

Amendment 1

Clarification of definition of End of Trial for reporting purposes
 
Applicable Sections:
 
Section 4.1 Clinical Study Design
 
Subheading 4.1.1 added with clarified definition of end of trial
 
Additional subheading 4.1.2 added for the subsection on Guidance for dose modification in case of adverse events

The protocol was amended to require discontinuation when the criteria of liver enzymes AST or ALT $\geq 1.5 \times$ ULN and / or total bilirubin $\geq 1.5 \times$ ULN is met at Visit 3,
 
Applicable Sections:
 
Section 4.1.2, Section 4.5.4, Appendix 9

Reference to description of highly effective contraception/preventive exposure measures in Section 4.5.3.1 Precautions for Sexual Intercourse added to Inclusion criterion 11.
 
Applicable Section:
 
Section 4.5.1 Inclusion Criteria

Exclusion Criteria 2 and 21 combined into revised exclusion criterion 2
 
Replacement of exclusion criterion 21 with criterion [REDACTED]
 
Applicable Section:
 
Section 4.5.2 Exclusion Criteria


Discontinuation to be mandatory for specified safety findings.
 
Applicable Section:
 
Section 4.5.4, Subsection: Discontinuation of IMP
 
The wording “should be discontinued” was replaced by “will be discontinued”.

Specification that statistical testing will be 2-sided.
 
Applicable Sections:
 
Section 7.1, Section 7.3.4

Amendment 1
Rationale for the sample size was added. Applicable Section: Section 7.1
Clarification of the planned pooled data analysis of the two identical studies, GLPG1690-CL-303 and GLPG1690-CL-304 Applicable Section: Section 7.3.4
The language related to the Declaration of Helsinki was updated to conform with EU Directives 2001/20/EC and 2005/28/EC Applicable Sections: Section 10
The procedure for collection of informed consent of a patient unable to read and/or write was amended [REDACTED] Applicable Section: Section 10.4.2

Update 1
Minor edits and edits based on ad hoc IB update – General

LIST OF ABBREVIATIONS AND DEFINITION OF TERMS

Abbreviations

%FEV ₁	percent predicted forced expiratory volume in 1 second
%FVC	percent predicted forced vital capacity
6MWT	6-Minute Walk Test
AE	adverse event
ALAT	Latin American Thoracic Association
ALT	alanine aminotransferase
AST	aspartate aminotransferase
AT1	angiotensin II receptor type 1
ATC	Anatomical Therapeutic Classification
ATS	American Thoracic Society
ATX	autotaxin
AUC	area under the plasma concentration-time curve
AUC _{0-∞}	area under the concentration-time curve from time 0 to infinity
AUC _{0-24h}	area under the plasma concentration-time curve from time 0 to 24 hours
BLM	bleomycin
BCRP	breast cancer resistance protein
b.i.d.	bis in die, twice daily
BSEP	bile salt export pump
BW	body weight
C _{Cr}	estimated creatinine clearance, calculated according to Cockcroft-Gault calculation
CEAC	clinical endpoint adjudication committee
CK	creatine kinase
C _{max}	maximum observed plasma concentration
COVID-19	Coronavirus disease
CRO	contract research organization
CRF	case report form
CTCAE	Common Terminology Criteria for Adverse Events
CTFG	Clinical Trial Facilitation Group
CTGF	connective tissue growth factor
CYP	cytochrome P450

DBP	diastolic blood pressure
DDI	drug-drug interaction
DLCO	diffusing capacity of the lung for carbon monoxide
DTP	direct-to-patient
ECG	electrocardiogram
E _{max}	maximum effect (expressed as a percentage reduction from baseline)
ENPP1/2	ectonucleotide pyrophosphatase/phosphodiesterase 1 or 2
eCOA	electronic clinical outcome assessment
EoSA	end of study assessments
EoST	end of study treatment
EQ-5D	EuroQOL 5-Dimensions Questionnaire
EQ-5D-3L	3-level version of EuroQOL 5-Dimensions Questionnaire
EQ VAS	EuroQOL visual analogue scale
ERS	European Respiratory Society
ETD	early treatment discontinuation
FAS	full analysis set
FC	food consumption
	
FEF ₂₅₋₇₅	forced expiratory flow between 25% and 75% of exhaled volume
FEV ₁	forced expiratory volume in 1 second
FIH	first-in-human
FSH	follicle-stimulating hormone
FVC	forced vital capacity
GCP	Good Clinical Practice
GMP	Good Manufacturing Practices
GLP	Good Laboratory Practice
GGT	gamma glutamyl transferase
Hb	hemoglobin
HIV	human immunodeficiency virus
HMA	Heads of Medicines Agencies
HRCT	high-resolution computed tomography
IB	Investigator's Brochure
IC ₅₀	50% inhibitory concentration (concentration resulting in 50% inhibition)

IC ₈₀	80% inhibitory concentration (concentration resulting in 80% inhibition)
ICF	informed consent form
ICH	International Council for Harmonisation of Technical Requirements for Pharmaceuticals for Human Use
IDMC	independent data monitoring committee
IEC	Independent Ethics Committee
I _{max}	predicted maximum concentration in the portal vein
IMP	investigational medicinal product
INR	International Normalized Ratio
IPF	idiopathic pulmonary fibrosis
IRB	Institutional Review Board
IWRS	interactive web response system
JRS	Japanese Respiratory Society
K-BILD	King's Brief Interstitial Lung Disease
LB	lung biopsy
LC-MS/MS	liquid chromatography with tandem mass spectrometry
LCQ	Leicester Cough Questionnaire
LFT	liver function test
LPA	lysophosphatidic acid
LPC	lysophosphatidylcholine
LPD	lysophospholipase D
MCID	Minimal Clinical Important Difference
MCH	mean corpuscular hemoglobin
MCHC	mean corpuscular hemoglobin concentration
MCV	mean corpuscular volume
MedDRA	Medical Dictionary for Regulatory Activities
NOAEL	no observed adverse effects level
OATP	organic anion transporting polypeptide
OCT1	organic cation transporter 1
■	■
PDE	phosphodiesterase
P-gp	P-glycoprotein
PK	pharmacokinetic(s)
PLA	phospholipase A

PLC	phospholipase C
q.d.	quaque die, once daily
QTc	corrected QT interval
QTcF	QT interval corrected for heart rate using Fridericia's formula
QTcV	QT interval corrected for heart rate using Van de Water's formula
SAE	serious adverse event
SAP	statistical analysis plan
SBP	systolic blood pressure
SD	standard deviation
SGRQ	St. George's Respiratory Questionnaire
SpO ₂	oxygen saturation
SUSAR	suspected unexpected serious adverse reaction
t _{1/2}	terminal elimination half-life
TEAE	treatment-emergent adverse event
TGFβ	transforming growth factor β
t _{max}	time to maximum observed plasma concentration
UGT	uridine 5'-diphospho-glucuronosyltransferase
UIP-IPF	usual interstitial pneumonia – idiopathic pulmonary fibrosis
ULN	upper limit of the normal range
VAS	Visual Analogue Scale
V _{ss}	volume of distribution at steady state
WBC	white blood cell
WHO	World Health Organization
WOCBP	women of child bearing potential

Definition of Terms

BMI	weight (kg) / (height [m]) ²
C _{Cr}	estimated creatinine clearance, calculated according to Cockcroft-Gault calculation: $C_{Cr} \text{ (in mL/min)} = [(140 - \text{age}) \times \text{weight}] / [72 \times S_{Cr}] \text{ (x 0.85 for women)}$, with S _{Cr} = serum creatinine in mg/dL, age in years and weight in kg
QTcF	QT interval corrected for heart rate using Fridericia's formula: $QTcF = QT / RR^{1/2}$, with RR = mean interval duration between consecutive RR peaks
QTcV	QT interval corrected for heart rate using Van de Water's formula: $QTcV = QT - 0.087 (60 / HR - 1)$, with HR = heart rate

